5.2 Interim Analyses and Data Monitoring

There will be no interim analysis. Data will be monitored and queried throughout the study.

5.3 Multicenter Studies

The centers will be pooled for analysis.

5.4 Multiple Comparisons / Multiplicity

There are 2 treatment arms and 1 primary endpoint. There will be no adjustments for multiple comparisons or multiplicity.

6. SUMMARY OF STUDY POPULATION DATA

6.1 Subject Disposition

The number and percentage of subjects completing the study and terminating early, with the reason for termination, will be summarized for each treatment group and overall for the Safety Population. Summary statistics for subjects randomized, and in each study population and reasons for exclusion from the ITT and PP Populations will be provided for each treatment group and overall for all screened subjects. The percentages for the summaries of the number of subjects in each study population will be based on the number of subjects in the Safety Population. Protocol deviations will be listed.

6.2 Demographics and Baseline Characteristics

Demographic and baseline characteristics will be summarized using descriptive statistics (for continuous variables) or frequency/percentage (for categorical variables), by treatment group and overall. Medical and surgical history will be listed for the Safety Population. Adverse events that are not treatment emergent (occur before treatment) will be listed by Safety Population.

6.3 Dosing and Extent of Exposure

Exposure and compliance will be summarized for the Safety Population by treatment group and overall. Comments recorded on the Compliance CRF page regarding dosing will not be applied in the computation of compliance. Exposure is the duration (days) of treatment, computed as:

Exposure= Date of Final Dose- Date of Baseline Visit + 1.

Treatment compliance will be calculated as:

Compliance (%) = 100*(Total Number of Capsules Dispensed-Total Number of Capsules Returned)/Exposure.

Summary statistics for exposure and compliance will be presented in a table with the corresponding listing for the Safety Population.

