# 7.7 Dietary Requirements

Multiple food effect studies have demonstrated that high fat, protein or carbohydrate meals all had a similar effect of decreasing the maximum serum concentration ( $C_{max}$ ) (average of 80-90%),

prolonging the time of maximum plasma concentration ( $T_{max}$ ) (8-12 fold), and decreasing the area under the concentration time-curves from time zero to infinity ( $AUC_{0-\infty}$ ) of ifetroban (average of 25-35%) compared to the fasting state.

For this reason, ifetroban and placebo should be taken at least 30 minutes before a meal or six hours after a meal.

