#### If the subject meets all inclusion and does not meet any exclusion criteria:

- Subject will be randomized
- PNIFR and FeNO will be recorded
- Perform serum/urine pregnancy test (for women of childbearing potential). Confirm subject is protected by one of the following acceptable forms of effective contraception during the study:
  - Established use of oral, injected or implanted hormonal contraceptive
  - "Double barrier" methods (i.e., Double Intrauterine device with copper or intrauterine system with progestogen and barrier contraceptive [condom, diaphragm or cervical/vault caps] used with spermicide [foam, gel, film, cream or suppository])
  - Female sterilization (e.g., tubal occlusion, hysterectomy or bilateral salpingectomy)
  - Male sterilization with post-vasectomy documentation of the absence of sperm in the ejaculate; for female subjects enrolled in the study, the vasectomized male partner should be the sole partner for that subject
- Perform blood sampling (prior to administration of IMP) for clinical laboratories: hematology, chemistry, PT, and INR.

Note: Clinical laboratory testing at Week 0 Visit is limited to biomarkers in serum and plasma if screening labs were performed within three weeks of starting IMP treatment.

- Collect urine and blood samples for eicosanoid metabolites.
- Collect nasoabsorptive matrix for eicosanoid measurements.

- Conduct a smell test (UPSIT)
- Collect data from subject diary and remind subject to record daily medication usage including IMP, exacerbations, rescue medication or antibiotic usage, if applicable, twice daily TNSS (AM and PM) and to bring their diary to the next visit
- Pre-IMP Dietary Assessment
- Dispense IMP and administer IMP
- Commence AE reporting
- Schedule appointment for next visit

Treatment Period (Week 0 to Week 8): Subjects will take ifetroban or placebo daily for eight weeks. There will be a telephone encounter one week into this Treatment Period to ensure safety and confirm that baseline asthma symptoms have not worsened.

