#### **Week 4 Treatment Visit**

After four weeks of treatment, subjects will return to the site for Week 4 Treatment Visit.

- Record all medication use with start date and dose and check for prohibited medications.
- Inquire about AEs/Serious Adverse Events (SAEs) and IMP tolerability
- Perform a limited physical exam with vital signs (blood pressure, heart rate, respiration rate, body temperature, weight)
- Administer TNSS, ACQ-7, and SNOT-22
- Obtain spirometry, PNIFR and FeNO
- Perform serum/urine pregnancy test (for women of childbearing potential) Confirm subject is protected by one of the following acceptable forms of effective contraception during the study:
  - Established use of oral, injected or implanted hormonal contraceptive
  - "Double barrier" methods (i.e., Double Intrauterine device with copper or intrauterine system with progestogen and barrier contraceptive [condom, diaphragm or cervical/vault caps] used with spermicide [foam, gel, film, cream or suppository])

- Female sterilization (e.g., tubal occlusion, hysterectomy or bilateral salpingectomy)
- Male sterilization with post-vasectomy documentation of the absence of sperm in the ejaculate; for female subjects enrolled in the study, the vasectomized male partner should be the sole partner for that subject
- Collect urine and blood samples for eicosanoid metabolites.
- Collect nasoabsorptive matrix for eicosanoid measurements.
- Conduct a smell test (UPSIT)
- Review subject diary for IMP compliance, content and completeness; collect data from subject diary and remind subject to continue recording daily medication usage including IMP, time of meals and doses, exacerbations, rescue medication or antibiotic usage (if applicable), twice daily TNSS (AM and PM) and to bring their diary to the next visit
- Dispense IMP and administer IMP
- Schedule appointment for next visit

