### 11.1 Sample Size Determination

Thirty-eight subjects per group will provide 90% power for the comparison of ifetroban and placebo with respect to the change from baseline in SNOT-22 scores at Week 8 (two-sided, level 0.05), assuming a common standard deviation of 16 and a true difference is 12.

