4.5 Sample Size Determination

Thirty-eight subjects per group will provide 90% power for the comparison of ifetroban and placebo with respect to the change from baseline in SNOT-22 scores at Week 8 (two-sided, level 0.05), assuming a common standard deviation of 16 and a true difference is 12.

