4.7 ANALYSIS POPULATIONS

Safety Population All subjects who received at least one dose of study medication will be included in the Safety Population.

Intent-to-Treat Population The Intent-To-Treat (ITT) Population will consist of all treated subjects with at least one post-baseline assessment of SNOT-22.

Per Protocol Population The Per Protocol (PP) Population will consist of all subjects in the ITT population with no major protocol violations, including violation of inclusion or exclusion criteria or insufficient dosing. Inclusion of subjects in the PP Population will be determined prior to unblinding.

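### Protocol 7.7 reports a large food effect and the diary collects meal and dose times, but compliance is a capsule count and no planned variable or stated Per Protocol rule uses those times

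*SAP*

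**What the plan says.** **Food effect.** Protocol 7.7 reports that meals of each type tested "had a similar effect of decreasing the maximum serum concentration", by 80–90% on average. Tmax is prolonged 8–12 fold and AUC falls by 25–35%. The section gives this as its reason for a meal-timing instruction that applies to both arms.

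**Data collected.** At the Week 4 visit subjects are reminded to "continue recording daily medication usage including IMP, time of meals and doses, exacerbations" and so on. The Week 8 list again names meal and dose times. At both visits the site reviews the diary for compliance. The Week 0 list differs: "remind subject to record daily medication usage including IMP, exacerbations, rescue medication or antibiotic usage, if applicable, twice daily TNSS". It does not mention meal times or dose times, although the same visit includes a dietary assessment before the first dose.

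**What is derived.** SAP 6.3 computes two dosing quantities. Exposure is the number of days from the baseline visit to the final dose, plus one. Compliance is capsules dispensed minus capsules returned, over exposure. The section also states: "Comments recorded on the Compliance CRF page regarding dosing will not be applied in the computation of compliance". Protocol 11.6.2 uses the same capsule count over four times exposure and likewise sets CRF comments aside. The variable list in SAP 4.6 contains nothing on meal timing.

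**Per Protocol set.** SAP 4.7 and Protocol 11.2.3 remove major violations, "including violation of inclusion or exclusion criteria or insufficient dosing", and membership is settled before unblinding. Insufficient dosing has no threshold, no data source and no stated link to the compliance percentage or to meals.

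**The concern.** By the protocol's own account, whether a dose is taken near a meal changes how much drug reaches the circulation. Correct dosing therefore has two parts here: taking the capsules, and taking them apart from food. The plan derives a measure of the first part only. The sentence about CRF comments is not the gap in itself; it closes one informal route by which irregular dosing might have entered the compliance figure.

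The reading of a null result is at stake. Protocol 5.3 calls this a proof-of-concept study, and the primary endpoint is analysed in two populations, ITT and Per Protocol. If neither shows an effect, the sponsor will ask whether the drug was given in a way that could work. The subject-level information for an answer is in the diary, but no planned summary draws on it.

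**Working it through.** **1. The plan's own figure.** SAP 4.5 states "Thirty-eight subjects per group will provide 90% power for the comparison of ifetroban and placebo", "two-sided, level 0.05), assuming a common standard deviation of 16 and a true difference is 12". The standard error of the difference is 16 × √(2/38) = 3.671, so the noncentrality is 12/3.671 = 3.269. With 74 degrees of freedom and a critical value of 1.993, power is 89.7% by the noncentral t and 90.5% by the normal approximation. The stated 90% reproduces.

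**2. What the compliance score sees.** Four capsules a day (Protocol 7.3) for 56 days is 224 capsules.

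| Capsules taken | Protocol 11.6.2: 100 × taken/(4 × 56) | SAP 6.3: 100 × taken/56 |
|---|---|---|
| 224 | 100% | 400% |
| 112 | 50% | 200% |
| 56 | 25% | 100% |

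The relation to meals enters neither formula, so 224 capsules taken fed and 224 taken fasted score the same. Under the SAP formula, 100% corresponds to one capsule a day. SAP section 9 does not list this as a change from the protocol.

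**3. Where the meal and dose times go.** They appear in the Week 4 and Week 8 visit lists. They do not appear in SAP 4.6 (variables), 6.3 (exposure and compliance), 4.7 (populations) or 7 (efficacy analyses). The general promises to list recorded data (SAP 5) and protocol deviations (SAP 6.1) would put them in a listing at most.

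**4. Coverage of Weeks 0–4.** The Week 0 reminder omits the times, while the Week 4 wording tells subjects to continue recording. The diary form is not in the documents. Collection in the first four of eight weeks is therefore uncertain.

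**5. Illustrative dilution.** The documents give neither the share of active subjects who dose fed (f) nor the share of effect lost by such subjects (L). Both are assumed here. Diluted difference = 12 × (1 − f × L). Power is by the noncentral t with 38 per group, SD held at 16, two-sided 0.05. L = 0.25 and 0.35 make the loss proportional to AUC; L = 1 is the extreme of no effect in fed subjects.

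| f | L | Difference | Power |
|---|---|---|---|
| 0 | – | 12.00 | 89.7% |
| 25% | 0.25 | 11.25 | 86% |
| 25% | 0.35 | 10.95 | 84% |
| 25% | 1 | 9.00 | 68% |
| 50% | 0.25 | 10.50 | 81% |
| 50% | 0.35 | 9.90 | 76% |
| 50% | 1 | 6.00 | 36% |

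**6. Which exposure measure matters.** Protocol 5.4 associates platelet inhibition with Cmax above 500 ng/mL but gives no Cmax at 200 mg. With 10–20% of fasted Cmax remaining, a fed dose would stay above 500 only if fasted Cmax exceeded 500/0.20 = 2,500 to 500/0.10 = 5,000 ng/mL. Loss of that level with food can be neither shown nor excluded, and the documents do not say whether Cmax or AUC drives an eight-week change in SNOT-22.

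**The case against.** Capsule counts are a common compliance measure, and leaving free-text comments out of one is ordinary practice. The primary analysis is ITT with LOCF, which keeps fed dosers by design, so the power figures describe a comparison that no change to SAP 6.3 would improve. On the AUC figures, 25% fed dosing costs only about 4 to 6 points of power. The plan also summarises eicosanoid biomarkers at Weeks 0, 4, 8 and 10, which give indirect evidence on whether the drug was acting. All of this stands. It limits the point to how the result is read, and it rules out saying that the planned outputs carry no information on drug action. The biomarkers still do not show how a subject's doses related to meals, and Table 8–1 lists no ifetroban concentration sample.

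Three stronger readings are tempting, and the documents do not support them.

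- A reader might infer that the Per Protocol set is built on the capsule count and so retains under-exposed subjects. The definition is not tied to the compliance percentage, and the review before unblinding could treat repeated fed dosing as a violation. The plan does not say whether it will.
- A reader might infer that no meal times exist for Weeks 0–4. The word continue at Week 4 points the other way.
- A reader might describe fed doses as unabsorbed. The protocol's figures leave 65–75% of AUC.

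**Conclusion.** The point holds as a gap between what the protocol says matters, what it collects and what the SAP uses. Food lowers Cmax by 80–90% and AUC by 25–35%, meal and dose times are requested, and no derived variable, planned summary or stated Per Protocol rule draws on them. Compliance and exposure are both blind to food.

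The effect on the trial result cannot be computed from the documents. Under assumed fed shares of 25% and 50%, power for the primary comparison would be 84–86% and 76–81% if effect follows AUC, and 68% and 36% if fed subjects lose all effect, against 89.7% as planned. These figures rest wholly on the assumed shares and losses and on an unchanged SD of 16. They show why the information is worth having and are not a loss that the fix would reverse.

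The change is worth making because it is cheap and mostly uses data that the protocol already asks for. The missing factor of 4 in SAP 6.3 is a separate contradiction with Protocol 11.6.2, and the two passages must be reconciled.

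**What to change.** 1. Add meal and dose times to the Week 0 diary instruction, so that it matches Weeks 4 and 8.
2. In SAP 6.3, derive for each subject the percentage of recorded doses that meet the Protocol 7.7 instruction, and tabulate it by arm beside capsule compliance. The sponsor must first state how the two conditions joined by or in 7.7 are to be read together, because a dose shortly before one meal may also fall soon after another.
3. Use that percentage in the blinded review of insufficient dosing for the Per Protocol set, with the rule written down before unblinding, or in a supportive analysis of the primary endpoint.
4. Separately, reconcile the compliance formulas in SAP 6.3 and Protocol 11.6.2.

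The cost is one diary phrase, one derived variable and possibly a somewhat smaller Per Protocol set. If the diary change comes too late for enrolled subjects, steps 2 and 3 can still use the times already recorded. The ITT/LOCF primary analysis is unchanged.

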# 7.3 Drugs and Dosages

Oral ifetroban is available as the sodium salt of the free acid and is for investigational use only. The drug is supplied as a capsule dosage form (size # 1, white opaque) for oral administration. Ifetroban capsules are formulated as a dry powder blend and filled into hard gelatin capsules. The formulation consists of ifetroban, mannitol, microcrystalline cellulose, crospovidone, magnesium oxide, colloidal silicon dioxide, and magnesium stearate. Capsules are filled into high density polyethylene bottles and sealed with screw-cap closures. Capsules are only available at one strength of the sodium salt, i.e., 52.5 mg corresponding to a free-acid dose of 50 mg.

Matching placebo capsules are formulated as a dry powder blend filled into capsules. The formulation consists of microcrystalline cellulose, crospovidone, colloidal silicon dioxide, and magnesium stearate. Capsules are filled into high density polyethylene bottles and sealed with screw-cap closures.

The bottles of oral Ifetroban or placebo will contain the following information on the label:

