#### PLACEBO OR IFETROBAN CAPSULES 50MG

Quantity: 75 Capsules

Instruction: Take capsules by mouth as directed.

Store at controlled room temperature,  $20^{\circ}\text{C} - 25^{\circ}\text{C}$  ( $68^{\circ}\text{F} - 77^{\circ}\text{F}$ )

Caution: New Drug-Limited by Federal law to investigational use

Cumberland Pharmaceuticals Inc.

Additionally, each individual bottle will be labelled with a unique numeric code that identifies the contents to the unblinded sponsor representative. Four (4) capsules each of IMP (oral ifetroban or matching placebo) will be taken by mouth per daily dose during the Treatment Period.

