# 11.6.2 Exposure and Compliance

Exposure and compliance will be summarized for the Safety Population by treatment group and overall. Comments recorded on the Study Drug Accountability CRF page will not be applied in the computation of compliance.

Exposure is the duration (days) of treatment, computed as:

Exposure = Date of Final Dose- Date of Baseline Visit + 1.

Treatment compliance will be calculated as:

Compliance (%) = 100\*(Total Number of Capsules Dispensed-Total Number of Capsules Returned)/(4\*Exposure).

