1. INTRODUCTION

This Statistical Analysis Plan (SAP) is based on study procedures and analyses described in the protocol (dated 24 January 2017). Table shells and mock listings corresponding to the contents of this document will be included with the final version. This document, with table shells and mock listings, will be reviewed prior to any unblinded analyses, and revised if necessary.

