5. GENERAL STATISTICAL CONSIDERATIONS

The following text provides general description of the statistical methodology for the assessment of efficacy, safety, and tolerability of 200 mg/day of oral ifetroban in this double-blind placebo-controlled study in subjects with symptomatic AERD.

Appropriate summary statistics will be provided for categorical data (n, %) and for continuous data (n, mean, standard deviation, minimum, median, maximum). All recorded data will be listed by subject and by visit unless otherwise specified.

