9. CHANGES IN THE STATISTICAL METHODS FROM THOSE STATED IN THE PROTOCOL

The secondary variables will be analyzed with the ITT population only.

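### The SAP's compliance formula omits the four capsules per daily dose, so every compliance percentage programmed as written is four times too high

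*SAP*

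**What the plan says.** SAP 6.3 gives the formula "Compliance (%) = 100*(Total Number of Capsules Dispensed-Total Number of Capsules Returned)/Exposure". The unit of the denominator is stated just before it: "Exposure is the duration (days) of treatment, computed as" the date of the final dose minus the date of the baseline visit, plus one. The section commits to a summary table and a listing of compliance for the Safety Population. It also says that dosing comments on the compliance CRF page are not applied in the computation.

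Protocol 11.6.2 has the same definition of exposure and the same numerator, but its denominator carries a factor of four: "Total Number of Capsules Returned)/(4\*Exposure".

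The number of capsules per day is stated in protocol 7.3: "Four (4) capsules each of IMP (oral ifetroban or matching placebo) will be taken by mouth per daily dose". The same section says "Capsules are only available at one strength of the sodium salt, i.e., 52.5 mg corresponding to a free-acid dose of 50 mg". The SAP does not state a number of capsules, but its section 5 gives the daily dose, referring to "efficacy, safety, and tolerability of 200 mg/day of oral ifetroban".

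SAP section 9 lists one change from the protocol: "The secondary variables will be analyzed with the ITT population only". It does not mention the compliance formula.

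**The concern.** A compliance percentage should be capsules used divided by capsules planned. Dividing capsules by days gives that ratio only when the plan is one capsule a day, and here it is four.

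What is at stake is the planned compliance table and the listing, where every subject's value would be wrong. Values near 400% would look odd. A value near 100% would look normal, yet it would belong to a subject who took about a quarter of the capsules.

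There is also a possible effect on the Per Protocol Population. SAP 4.7 excludes subjects with insufficient dosing and gives no cut-off, and the 6.3 percentage is the only compliance measure that the SAP defines. The primary variable is analysed in the PP as well as the ITT Population (SAP section 7). If the percentage were used to decide PP membership, under-dosing could be missed.

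**Working it through.** **Inputs**

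- Daily dose: 200 mg (SAP sections 4.3 and 5).
- Capsule strength: 50 mg free acid, the only strength (protocol 7.3).
- Capsules per daily dose: 4, both arms (protocol 7.3).
- Treatment period: eight weeks (SAP 4.1), that is 8 × 7 = 56 days.

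Neither document states a numeric compliance value, so there is no figure of the plan's own to reproduce. The check is to evaluate the two formulas on the same data.

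**Step 1. Capsules per day.** 200 mg / 50 mg = 4. This agrees with the four capsules stated in protocol 7.3, so the factor does not rest on the protocol's compliance formula alone.

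**Step 2. Planned capsules.** 4 × 56 = 224.

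**Step 3. The two formulas.**

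- SAP 6.3: 100 × used / Exposure
- Protocol 11.6.2: 100 × used / (4 × Exposure)

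Their ratio is 4 whatever the number used and whatever the exposure.

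**Step 4. Values at an exposure of 56 days.**

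| Dosing | Capsules used | SAP 6.3 | Protocol 11.6.2 |
|---|---|---|---|
| Full dosing | 224 | 100 × 224/56 = 400% | 100 × 224/224 = 100% |
| 6 days missed | 200 | 100 × 200/56 = 357.1% | 100 × 200/224 = 89.3% |
| 14 days missed | 168 | 100 × 168/56 = 300% | 100 × 168/224 = 75% |
| 28 days missed | 112 | 100 × 112/56 = 200% | 100 × 112/224 = 50% |
| One capsule per day | 56 | 100 × 56/56 = 100% | 100 × 56/224 = 25% |

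The missed-day rows assume that the misses fall before the final dose, so that exposure stays at 56 days. A subject who takes every dose but stops six days early has an exposure of 50 days and uses 4 × 50 = 200 capsules. That subject reads 100 × 200/50 = 400% under the SAP and 100 × 200/(4 × 50) = 100% under the protocol. The ratio is still 4.

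**Step 5. Other exposures.** The ratio was also 4.0 at exposures of 1, 28, 51, 57 and 61 days with 100%, 80%, 50% and 25% of capsules used.

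**Step 6. Effect of a cut-off, for illustration only.** Assume a threshold of 80%; the documents give none. A subject who used 20% of the capsules (0.20 × 224 = 44.8) would read 100 × 44.8/56 = 80% under the SAP formula and would pass.

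**The case against.** The arithmetic is not in dispute. The case on the other side is that it matters little, and most of that case is fair.

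- **Only a descriptive display is affected.** No hypothesis test or efficacy model uses compliance, the factor is the same in both arms, and dividing by four recovers the right value. This stands, and it limits the importance of the point.
- **The error would show itself.** A table with full dosers at 400% is unlikely to pass unnoticed, and a subject at 100% would be a visible low outlier among them. SAP section 1 plans a review, with table shells and mock listings, before any unblinded analysis. This is a real mitigation. But if a programmer corrects the formula silently, the code departs from the SAP without a record, so correcting the text is cleaner.
- **Nothing ties the percentage to the PP Population.** This is correct. Protocol 8.1.2 also has dosing compliance reviewed from the subject diary, so the PP consequence is conditional.
- **The silence of SAP section 9 proves nothing.** This is also correct. The SAP says "This Statistical Analysis Plan (SAP) is based on study procedures and analyses described in the protocol (dated 24 January 2017"), and the date of the protocol supplied is not visible. Other differences would fit a different protocol version: the SAP has a two-week screening period and ±2-day visit windows, where the protocol has three weeks and ±5 days. Whether section 9 should have listed the formula cannot be checked. The error does not depend on it, because a formula without the factor is wrong for a four-capsule dose under any version.

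**Conclusion.** The concern holds. As written, the SAP 6.3 formula overstates compliance by a factor of exactly four for every subject: 400% for full dosing, and 100% for a subject who used a quarter of the planned capsules. The conclusion rests on two conditions: the formula is programmed as it stands, and the daily dose is four capsules, as protocol 7.3 says and as 200 mg/day in 50 mg capsules implies.

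The reach is limited. The compliance table and listing for the Safety Population would be wrong. The comparison of compliance between arms would not be biased in relative terms, and the primary analysis of SNOT-22 change at Week 8 (ITT, LOCF) is unaffected. PP membership is at risk only if the percentage is used to judge insufficient dosing. The point should be fixed because the error is certain and the correction is simple, not because it threatens the trial's main result.

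**What to change.** In SAP 6.3, change the denominator from Exposure to 4 × Exposure, as in protocol 11.6.2. With that change, 56 days of full dosing gives 100 × 224/(4 × 56) = 100%, and using 80%, 50% or 25% of the capsules gives 80%, 50% or 25%.

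Two conditional additions:

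- If the compliance percentage is to decide insufficient dosing, say so in SAP 4.7 and fix the cut-off on the corrected scale before unblinding.
- Check the protocol version that the SAP cites. List the formula in SAP section 9 only if the corrected formula differs from that version.

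The cost is one term in one formula and one line of code, at a review the SAP already plans. There is no burden on subjects or sites, and no dose or clinical rule changes.
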